6.14.5.6. Infections

Infections will be defined using all the PTs from the Infections and Infestations SOC as defined in MedDRA. Serious infection will be defined as all the infections that meet the SAE criteria.

The number and percentage of patients with TEAEs of infections, serious infections, and infections resulting in permanent study drug discontinuation will be summarized by treatment group using MedDRA PTs. The proportion of patients developing skin infections requiring antibiotic treatment will also be summarized in the overview of infections table.

The number and percentage of patients with TEAEs of infections by maximum severity will be summarized by treatment group using MedDRA PTs.

The IR and 95% CI will be calculated for the overall observation time for infections of special interest (serious infections, treatment-emergent herpes zoster, treatment-emergent tuberculosis, treatment-emergent opportunistic infections [OIs]) for the final analysis.

Treatment-emergent infections may be reviewed in context of other clinical and laboratory parameters via a listing (for details, see compound-level safety standards).

The TEAE infections will be further analyzed in terms of OI, herpes zoster, and herpes simplex. A summary of hepatitis B virus (HBV) deoxyribonucleic acid (DNA) monitoring results and association between infection and neutropenia/lymphopenia will also be provided in the context of infections.

Opportunistic Infection

To identify OIs, the following approach will be used to identify the OIs using a list of MedDRA PTs (refer to the compound-level safety standards).

Potential opportunistic infections identified through search approaches will be combined in one list for medical assessment and final classification of whether the case met the modified Winthrop and colleagues (2015) definitions for OI.

A final listing or tabulation of OIs will be provided for the CSR and to assist the composition of patient narratives.

Herpes Zoster

Cases of herpes zoster will be further classified as follows:

- localized or nonmultidermatomal involvement of the primary and/or adjacent dermatomes only

- complicated – documented ocular (cornea or deeper structure; eg, iritis, keratitis, retinitis, etc.) or motor nerve involvement (eg, palsy; postherpetic neuralgia does not meet criteria for motor nerve involvement)
- uncomplicated, localized or nonmultidermatomal cases that are not complicated

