Skin Infections

A summary analysis of skin infections will be provided. Skin infections may be defined based on MedDRA PT (see the compound-level safety standards).

HBV DNA

A listing of patients with detectable HBV DNA postbaseline will be provided.

Hepatitis B virus DNA status postbaseline (not detectable, detectable but not quantifiable [ie, < lower limit of detection (LLOD)], quantifiable [ie, \geq LLOD]) will be summarized by treatment group stratified by baseline HBV serology status, specifically:

- HBsAb+/HBcAb+
- HBsAb-/HBcAb+

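### The HBV DNA summary uses the limit of detection to separate 'detectable but not quantifiable' from 'quantifiable', so the middle label contradicts its own definition

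*SAP*

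**What the plan says.** Under its HBV DNA subheading, SAP Section 6.14.5.6 plans two outputs.

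The first is a listing: "A listing of patients with detectable HBV DNA postbaseline will be provided".

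The second is a summary table with three statuses. It opens with "Hepatitis B virus DNA status postbaseline (not detectable, detectable but not quantifiable" and defines the upper two by a bracketed cut: "detectable but not quantifiable [ie, < lower limit of detection (LLOD)], quantifiable [ie", at or above the same limit. The table is then laid out by arm and serology: "LLOD]) will be summarized by treatment group stratified by baseline HBV serology status, specifically". The two strata named are both positive for hepatitis B core antibody (HBcAb); one is positive and the other negative for surface antibody.

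Earlier in the same section the table is announced in general terms: "A summary of hepatitis B virus (HBV) deoxyribonucleic acid (DNA) monitoring results and association between infection and neutropenia/lymphopenia will also be provided".

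The SAP spells out LLOD as the lower limit of detection. It gives no numeric or verbal rule for the undetected status, and it names no limit of quantification here or elsewhere.

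**The concern.** Detection and quantification are two different thresholds. A three-way classification into undetected, detected but too low to measure, and measurable needs a rule for each boundary. The SAP supplies one limit and puts it at the wrong boundary: the limit that decides whether anything was detected is used to decide whether what was detected can be quantified.

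The bracketed text is the operative rule. Several neighbouring definitions in Section 6.14.5.6 (opportunistic infections, herpes simplex, skin infections) refer to the compound-level safety standards. The HBV DNA paragraph makes no such reference, so a programmer has only these words to work from.

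What is at stake is how a low-level signal reads in HBcAb-positive patients. The middle category exists to keep such a signal apart from a measurable viral load. Two programmers following the text could produce different tables: one guided by the verbal labels, the other by the bracketed cut.

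**Working it through.** No sample size, power, alpha or event count is involved, so the check is logical. The inputs are the three labels and the single cut in Section 6.14.5.6.

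Let L be the limit of detection and Q the limit of quantification, with Q at or above L. The SAP gives neither value. Each kind of laboratory result is placed first by the verbal label and then by the bracketed cut.

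| Result | By the verbal label | By the bracketed cut | Agree? |
|---|---|---|---|
| (a) Target not detected | not detectable | below L, so detectable but not quantifiable | No |
| (b) Signal reported although below the nominal L (only if the assay reports such results) | detectable but not quantifiable | below L, so detectable but not quantifiable | Yes |
| (c) Detected, at or above L but below Q | detectable but not quantifiable | at or above L, so quantifiable | No |
| (d) At or above Q | quantifiable | at or above L, so quantifiable | Yes |

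Three things follow.

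1. The two numeric rules, below L and at or above L, already cover every possible value. No numeric room is left for the undetected status, so a result of type (a) meets the rule for one category and the label of another. That is the overlap.
2. Results of type (c) are the ordinary content of the middle category, and the cut sends them to the top one. If Q equals L, type (c) is empty and nothing is misplaced at this boundary.
3. The rules and labels agree for every kind of result only if the upper cut is Q and the undetected status has its own rule. The categories are then: target not detected; detected and below Q; at or above Q.

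The number of misplaced results is the count of type (c), plus the count of type (a) if the cut is applied literally to undetected results. Finding either count requires data the SAP does not contain: L, Q, the number of HBcAb-positive patients, and their postbaseline results.

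The scope of the output comes from three other sections. Section 6.14 lists what is analysed at the final lock; an overview of infections is there, an HBV DNA table is not. Section 6.14.5 leaves analyses of adverse events of special interest out of the final lock and relies on integrated summaries. Section 6.2.1 reports the Week 16 lock as already executed.

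**The case against.** The strongest reply is that the undetected status is listed separately and carries no number. The three statuses can then be read as exclusive and exhaustive: no target detected; detected, but below the stated limit; at or above it. An assay may report a signal below its nominal detection limit, as in row (b), so the middle category need not be empty. This stands to the extent that a reader should not infer the category is impossible; that would depend on an assay property the SAP does not state. It does not rescue the cut. Even on this reading, results of type (c) are called quantifiable, and the SAP gives no rule for assigning the undetected status.

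A reader might also infer that all low-level results are misreported. The documents do not support that as a fact. Misplacement at the upper boundary requires Q to exceed L, and the SAP is silent on both.

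A third tempting inference is that negative results would fill the patient listing. The listing sentence speaks only of detectable DNA and carries no LLOD cut. If it is built from the laboratory's detected or not-detected result, it is unaffected.

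Finally, it can be said that the table is descriptive, that the listing stands beside it, and that this SAP version was approved before the final lock, at which the table appears not to be produced. All of that stands. It limits the size of the problem without making the definition right.

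**Conclusion.** The definition is wrong as written. One limit, of detection, separates two statuses that differ by quantification; the middle label contradicts its cut; and the middle and lowest categories overlap.

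The severity is minor. No test, alpha, power, efficacy endpoint or estimand depends on this table. Its reach is the Week 16 and interim outputs and any integrated summary that takes over the wording. The number of affected results cannot be stated, and it could be zero if the two assay limits coincide and undetected results were assigned by label.

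The conclusion that the label and cut conflict rests on the SAP text alone. The conclusion that results would be reported as quantifiable when they are not rests on the assumption that the assay's limit of quantification is above its limit of detection.

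**What to change.** In Section 6.14.5.6, redefine the three statuses as:

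- *not detectable*: target not detected;
- *detectable but not quantifiable*: detected, below the lower limit of quantification;
- *quantifiable*: at or above the lower limit of quantification.

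State that the patient listing takes the second and third categories. Confirm how any table already produced for the Week 16 or interim locks was programmed, and correct it if the detection limit was used as the cut. Check that integrated summaries do not carry the same wording.

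The cost is one line of SAP text and a check of the program. No new data need be collected if the laboratory result already shows whether the target was detected and whether it was quantified. The SAP does not say so, and this should be verified.

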6.14.5.7. Major Cardiovascular Events and other Cardiovascular Events

Potential major cardiovascular events (MACE) and other cardiovascular events requiring adjudication will be analyzed.

Categories and subcategories analyzed will include, but are not limited to, the following:

- major cardiovascular events
 - cardiovascular death
 - myocardial infarction
 - stroke
- other cardiovascular events
 - transient ischemic attack
 - hospitalization for unstable angina
 - hospitalization for heart failure
 - serious arrhythmia
 - resuscitated sudden death
 - cardiogenic shock
 - coronary revascularization (such as coronary artery bypass surgery or percutaneous coronary intervention)
- noncardiovascular death
- all-cause death

In general, events requiring adjudication are documented by investigative sites using an endpoint-reporting CRF. This CRF is then sent to the adjudication center which uses an adjudication-reporting CRF to document the final assessment of the event as a MACE, as some other cardiovascular event, or as no event (according to the Clinical Endpoint Committee Charter). In some cases, however, the investigator may not have deemed that an event had met the endpoint criteria but the event was still sent for adjudication as a potential MACE, other

cardiovascular event, or no event. These events are included in the adjudication process to ensure adequate sensitivity. In these instances, the adjudication-reporting CRF will not have a matching endpoint-reporting CRF from the investigator. Events generated from these circumstances will be considered as events sent for adjudication in the absence of an investigator's endpoint-reporting form.

The number and percentage of patients with MACE, other cardiovascular events, noncardiovascular death, and all-cause death, as positively adjudicated, will be summarized by treatment group based on the categories and subcategories above.

A listing of the events sent for adjudication will be provided to include data concerning the MedDRA PT related to the event, the seriousness of the event, and the event outcome, along with the adjudicated result.

6.14.5.8. Venous Thromboembolic Events

Events identified as representative of venous thromboembolic event (VTE) disease will be further classified as deep vein thrombosis (DVT), pulmonary embolism (PE), or other peripheral venous thrombosis and will be analyzed. The following definitions apply:

- DVT: Clinical diagnosis of a thrombosis in a deep vein above the knee that must be confirmed by objective evidence of either a filling defect of deep veins of the leg on venography or a noncompressible venous segment on ultrasound or confirmation by other imaging modality (eg, computed tomography [CT] scan, magnetic resonance imaging [MRI]).
- PE: Clinical diagnosis of pulmonary embolus that must be confirmed by objective evidence of either a filling defect of pulmonary arteries by either pulmonary angiography or CT angiography or by a high-probability ventilation perfusion scan.
- Other peripheral venous thrombosis: Clinical diagnosis of a venous thrombosis not specified by either DVT or PE above. Other peripheral venous thrombosis must be confirmed by objective evidence by imaging including venography, ultrasound, CT scan, or MRI. Examples of these would include nonsuperficial below knee thrombosis, portal vein, subclavian vein, or mesenteric vein. Superficial thrombophlebitis alone is not considered a VTE event.

In general, events requiring adjudication are documented by investigative sites using an endpoint-reporting CRF. Refer to Section 6.14.5.7 for more details as the process is the same as that of MACE.

The number and percentage of patients with a VTE, DVT/PE, DVT, PE, and other peripheral venous thrombosis, as positively adjudicated, will be summarized by treatment group.

A listing of the VTE events sent for adjudication will be provided to include data concerning the MedDRA PT related to the event, the seriousness of the event, and the event outcome, along with the adjudicated result.

6.14.5.9. Arterial Thromboembolic (ATE) Events

Refer to the compound-level safety standards.

6.14.5.10. Malignancies

Malignancies will be identified using terms from the malignant tumors SMQ (SMQ 20000194). Malignancies excluding non-melanoma skin cancers (NMSC) and NMSC alone will be reported separately.

All the cases identified by malignant tumors SMQ will be assessed thorough Medical (Global Patient Safety/Business Unit) / medical team review to determine confirmed NMSC cases.

First, a listing including all the malignancy cases will be prepared before database lock along with the *planned* NMSC flag according to the current MedDRA version PTs (the list will be updated depending on the MedDRA version used for analysis):

- squamous cell carcinoma of skin (10041834)
- Bowen's disease (10006059)
- basal cell carcinoma (10004146)
- basosquamous carcinoma (10004178)
- basosquamous carcinoma of skin (10004179)
- squamous cell carcinoma (10041823)
- skin squamous cell carcinoma metastatic (10077314)
- skin cancer (10040808)
- carcinoma in situ of skin (10007390)
- keratoacanthoma (10023347)
- vulvar squamous cell hyperplasia (10079905)
- skin squamous cell carcinoma recurrent (10081136)
- basal cell carcinoma metastatic (10083708)

This internal review is to occur prior to database lock. The case review and subsequent summary analyses will include all the cases reported in the study database or by Lilly Safety System report, disregarding the length of gap between the last treatment dose date and the event date. The NMSC flag will be confirmed by the medical team during the internal review process.

The number and percentage of patients with TEAEs associated malignancies excluding NMSC and NMSC will be summarized by treatment group.

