5. Study Design

Study I4V-MC-JAIW (JAIW) is a multicenter, randomized, double-blind, placebo-controlled, parallel-group, outpatient Phase 3 study evaluating the efficacy and safety of baricitinib 1-mg QD and 2-mg QD as compared to placebo in adult patients with moderate to severe AD. The study is divided into 3 periods: a 5-week Screening Period, a 104-week Double-Blinded Treatment Period, and a 4-week Post-Treatment Follow-Up Period.

Approximately 450 patients aged ≥ 18 years who have responded inadequately to or who are intolerant of topical therapy will be randomized at a 1:1:1 ratio to receive placebo QD, baricitinib 1-mg QD, or baricitinib 2-mg QD (approximately 150 patients per group). Patients will be stratified at randomization according to disease severity (IGA 3 versus 4).

The primary and key secondary endpoints are assessed prior to or at Visit 8 (Week 16). At Week 16 those patients who met IGA 0 or 1 and who have not required rescue therapy prior to Week 16 will be allowed to continue in this study. All other patients will be discontinued from this study and may be eligible to enroll in a separate open-label study (Study JAIX). Patients experiencing worsening in disease severity resulting in an IGA score of ≥ 3 after Week 16 of Study JAIW will also have to be discontinued from this study and may be eligible to enroll in the open-label Study JAIX. Patients who complete Week 104 (Visit 15) will have the option to transition to open-label Study JAIX, if eligibility criteria are met regardless of responder status, or continue to the post-treatment follow-up.

Figure JAIW.5.1 illustrates the study design.

Abbreviations: AD = atopic dermatitis; QD = once daily; V = visit; W = week.

- ^a At Week 16, all patients who achieve an IGA 0 or 1 and who have not required rescue therapy before Week 16 will be allowed to continue in this study. All other patients will be discontinued from this study and may be eligible to enroll in the separate open-label Study JAIX.
- ^b Patients who complete this study will be eligible for assessment to enroll in open-label Study JAIX.
- ^c Occurs approximately 28 days after the last dose of investigational product.

Figure JAIW.5.1. Illustration of study design for I4V-MC-JAIW.

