Placebo	Placebo at entry to Study JAIW followed to data cut (interim clinical study report [CSR])
Baricitinib 1-mg	Baricitinib 1-mg at entry to Study JAIW followed to data cut (interim CSR)
Baricitinib 2-mg	Baricitinib 2-mg at entry to Study JAIW followed to data cut (interim CSR)

In the rare situation where a patient is lost to follow-up at the first postbaseline visit, but some safety data exists (eg, unscheduled laboratory assessments) after first dose of study drug, a listing of the data or a patient profile will be provided, when requested.

For the unblinded interim lock which is executed after all patients have completed the Week 16 visit (Visit 8) or discontinued, the efficacy analysis included up to Week 16 and the safety analysis will be up to Week 16 and selected analyses up to the data cut date.

For the final DBL, both efficacy and safety summaries will use the Week 16 Responders population. The data will be summarized from Week 16 to the final DBL, according to the treatment regimen to which patients were assigned at Week 16.

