6.14. Safety Analyses

The general methods used to summarize safety data, including the definition of baseline value, are described in Section 6.2.

Safety analyses will include data from , unless otherwise stated, and patients will be analyzed according to the investigational product to which they were randomized at Week 0 (Visit 2). Safety analyses will use the safety population defined in Section 6.2.2.

By-visit summaries will include planned on-treatment visits. For tables that summarize events (such as AEs, categorical lab abnormalities, shift to maximum severity), post-last dose follow-up data will be included. Follow-up data is defined as all data occurring up to 30 days (planned maximum follow-up time) after last dose of treatment including rescue, regardless of study period. Listings will include all safety data.

For the 16-week interim lock, all safety data up to the Week 16 visit and at time of the interim lock were included in the safety analysis. Safety data from patients who permanently discontinued study drug prior to time of the interim lock will be included in the interim lock safety analysis up to 30 days post-last dose of the study drug.

For the final DBL, safety data from the Week 16 visit date up to the end of the study will be included in the safety analysis. Safety data from patients who permanently discontinued study drug will be included in the safety analysis up to 30 days post-last dose of the study drug.

The following will be analyzed for the final DBL, based on Week 16 Responders:

- summary of study drug exposure
- overview of adverse events
- overview of infections
- summary of temporary interruptions of study drug
- summary of treatment-emergent adverse events
- serious adverse events, summary and listing, and
- adverse events leading to permanent discontinuation of study drug, summary and listing.

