6.14.2. Adverse Events

Adverse events are recorded in the eCRFs. Each AE will be coded to System Organ Class (SOC) and preferred term (PT) using the Medical Dictionary for Regulatory Activities (MedDRA) version that is current at the time of database lock. Severity of AEs is recorded as mild, moderate, or severe.

A TEAE is defined as an event that either first occurred or worsened in severity after the first dose of study treatment and on or prior to the last visit date during the analysis period. The analysis period is defined as the treatment period plus up to 30 days off-drug follow-up time.

A TEAE defined for the final DBL (Week 16 to end of study) is defined as an event that either first occurred or worsened in severity after the Week 16 visit date and on or prior to the last visit date during the analysis period. The analysis period is defined as the treatment period from the Week 16 visit date plus up to 30 days off-drug follow-up time. The baseline severity is defined as the most severity in the baseline period that is between the first dose date and the Week 16 visit date.

Adverse events are classified based upon the MedDRA PT. The MedDRA Lowest Level Term (LLT) will be used in defining which events are treatment-emergent. The maximum severity for each LLT during the baseline period up to first dose of the study medication will be used as baseline. If an event with missing severity is preexisting during the baseline period, and persists during the treatment period, then the baseline severity will be considered mild for determining treatment emergence (ie, the event is treatment-emergent if the severity is coded moderate or severe postbaseline and not treatment-emergent if the severity is coded mild postbaseline). If an event occurring postbaseline has a missing severity rating, then the event is considered treatment-emergent, unless the baseline rating is severe, in which case the event is not treatment-emergent. The day and time for events where onset is on the day of the first dose of study

treatment will both be used to distinguish between pretreatment and posttreatment in order to derive treatment emergence. Should there be insufficient data for AE start date to make this comparison (eg, the AE start year is the same as the treatment start year, but the AE start month and day are missing), the AE will be considered treatment-emergent.

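### The malignancy section gives two conflicting time windows for its table, and neither ends at entry into open-label Study JAIX

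*SAP*

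**What the plan says.** Four parts of the SAP bear on this point.

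- **Which cases (Section 6.14.5.10).** The case review and the summary analyses that follow it draw on "all the cases reported in the study database or by Lilly Safety System report". No time limit is set, since cases are to be counted "disregarding the length of gap between the last treatment dose date and the event date". The last sentence of the section then specifies the only table: "The number and percentage of patients with TEAEs associated malignancies excluding NMSC and NMSC will be summarized by treatment group".
- **What treatment-emergent means (Sections 6.14.2 and 6.14).** Section 6.14.2 states: "The analysis period is defined as the treatment period plus up to 30 days off-drug follow-up time". The event must also fall on or before the last visit in that period. Section 6.14 sets the same limit for event tables: "Follow-up data is defined as all data occurring up to 30 days (planned maximum follow-up time) after last dose of treatment including rescue". It applies that limit whatever the study period.
- **Attribution (Sections 6.14 and 6.2.2).** In the safety analyses, "patients will be analyzed according to the investigational product to which they were randomized at Week 0 (Visit 2". Section 6.2.2 defines the interim placebo group as "Placebo at entry to Study JAIW followed to data cut (interim clinical study report [CSR"; entry into JAIX is not named as an end.
- **Route into JAIX (Section 5).** Patients with IGA 0 or 1 and no rescue continue after Week 16. For the rest: "All other patients will be discontinued from this study and may be eligible to enroll in a separate open-label study (Study JAIX".

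Section 6.14.5 omits analyses of adverse events of special interest from the final lock and relies on integrated summaries. Section 6.14's list of final-lock safety analyses does not name malignancies either.

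**The concern.** Ignoring the gap since last dose is a defensible choice for a long-latency event when patients leave a trial for no further study treatment. Here, patients who do not qualify to continue at Week 16 are removed from JAIW and may go straight into an open-label study. Time after their last JAIW dose may then be time on JAIX treatment. A rule that keeps counting under the randomised arm can label a cancer that arose during JAIX as a placebo case, or as a case on a JAIW dose the patient no longer takes.

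The unresolved window adds to this. Two programmers working from the same section could produce different tables, one with no time limit and one with a 30-day limit. Malignancy counts in a trial of this size will be very small, so a single case handled differently changes the comparison.

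**Working it through.** **1. Do the two sentences agree?** They could be reconciled if the unlimited rule governed only the case review and the 30-day rule governed the table. The wording blocks this, because the unlimited sentence names the summary analyses as well as the review. If the 30-day limit governs the table, that part of the sentence has no effect. If it does not, the table is not one of treatment-emergent events as Section 6.14.2 defines them. The SAP does not say which rule prevails.

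**2. Does either window stop at JAIX entry?**

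| | No-gap-limit reading | Treatment-emergent reading |
|---|---|---|
| Source | Section 6.14.5.10 | Sections 6.14.2 and 6.14 |
| Time after last JAIW dose | unlimited | up to 30 days, and not after the last visit in the period |
| Attribution | Week 0 arm | Week 0 arm |
| Cut at first JAIX dose | none stated | none stated |

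Under the second reading the exposure is short. It may be nil if only JAIW visits count as the last visit, which the SAP does not settle. By contrast, Section 6.2.1 does treat entry into JAIX as an end of JAIW participation for the final lock.

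**3. Which locks are exposed?** Section 6.2.1 puts three locks in scope: Week 16, the 4-month safety update and the final lock. Malignancy drops out of the final lock, as set out above. The Week 16 lock waits for the last patient's Week 16 visit, so patients enrolled earlier may already be in JAIX. Section 6.2.2 also allows selected safety analyses up to the data cut.

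**4. Size per case.** The SAP gives no malignancy figure to reproduce. The only input is about 150 patients per arm (Section 5). That size is consistent with the stated power in Section 6.1. For 10% versus 20%, the null standard error is √(2 × 0.15 × 0.85/150) = 0.0412 and the alternative standard error is √((0.09 + 0.16)/150) = 0.0408. Then z = (0.10 − 1.96 × 0.0412)/0.0408 = 0.47, giving power 0.681 against the stated 68%.

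- One case: 100 × 1/150 = 0.67 percentage points.
- Two cases on 2 mg against none on placebo: 1.33 − 0 = 1.33 points. With one JAIX-onset case counted under placebo: 1.33 − 0.67 = 0.67 points, half the difference.
- Three against none: 2.00 points, falling to 1.33 with one such case.

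**5. How many cases? (illustration on assumed inputs only)** Suppose 75 to 135 former placebo patients are in JAIX, with 0.3 to 1.0 malignancies per 100 patient-years. None of these figures is in the SAP. Expected extra placebo cases = patients × years × rate/100.

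- No limit, 0.25 to 1 year in JAIX: 75 × 0.25 × 0.3/100 = 0.06, up to 135 × 1 × 1.0/100 = 1.35.
- 30-day limit, with JAIX starting the day JAIW dosing ends: 75 × (30/365.25) × 0.3/100 = 0.02, up to 135 × (30/365.25) × 1.0/100 = 0.11.

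**The case against.** The strongest reply is that the operative sentence is the one that specifies the table. It counts treatment-emergent events, and the general rules give those a 30-day limit, so nearly all JAIX-onset cases fall outside. JAIX is a separate study, and nothing says that its cases enter the JAIW database or that the safety-system search extends into it. The final lock is not affected. Section 6.14.5.10 also requires a listing of all malignancies and a medical review before lock, and Section 6.14.5 provides patient profiles where needed, so a misplaced case could be noticed.

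Much of this stands, and it limits the point. It does not remove it. The unlimited sentence covers the summary analyses in terms, its second source of cases is not confined to JAIW time, and the 30-day window has no JAIX cut. The stated purpose of the review is to confirm non-melanoma skin cancers; it is not asked to reassign cases by treatment at onset.

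Three stronger readings are tempting, and the document supports none of them.

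- **That the SAP settles on counting malignancies with no time limit.** It does not; that is one of two conflicting sentences.
- **That a large share of the person-time behind the placebo count is open-label time.** The SAP gives no JAIX uptake or duration. Such a share would follow only from the unlimited reading, and this table reports numbers and percentages of patients, so person-time is not its denominator.
- **That the comparison is always pulled toward no difference.** The SAP does not state what JAIX gives, and patients leaving the baricitinib arms may enter JAIX too. Equal additions cancel in a difference of percentages: 2 versus 0 becomes 3 versus 1, still 1.33 points. They do shrink a ratio.

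**Conclusion.** The point holds as a contradiction plus a missing rule. Section 6.14.5.10 does not fix which malignancies are tabulated, and under either window a case with onset after the first JAIX dose could be attributed to the JAIW arm. The exposure is confined to the Week 16 and 4-month safety locks. Each such case is worth 0.67 points in an arm of about 150. The expected number is small on the assumed inputs, and smaller again if the 30-day limit governs. A diluted placebo comparison follows only if JAIX gives active drug and the former placebo patients contribute the extra cases, neither of which the SAP states. The reason to act is that one case can matter in a table of very few and that the repair is simple.

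**What to change.** In Section 6.14.5.10:

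1. State which window governs the malignancy table, and align the sentence on summary analyses with the one on treatment-emergent events.
2. Count a case under the randomised JAIW arm only if its onset precedes the first JAIX dose. An unlimited gap may be kept for patients who never enter JAIX.
3. List cases with onset on or after the first JAIX dose separately, showing the randomised arm and the treatment at onset.

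The cost is a few lines of SAP text and one comparison of onset date with first JAIX dose date, assuming the sponsor can link the two studies' records. The downside is that a few late cases move from the table to a listing; none is lost. The same change works whichever window is chosen.
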